### 7.4. Laboratory Procedures

Not Applicable.

## 8. SUBJECTS COMPLETION/WITHDRAWAL

### 8.1. Completion Criteria

Subjects are considered to have completed the study if they:

- provided informed consent.
- they are eligible.
- have not withdrawn/discontinued from the study for any reason described in section 8.2.
- completed all visits through the final visit 3.
- If all visits were completed but an additional visit is considered necessary for subject care, follow the requirements for unscheduled visits in section 7.3.

### 8.2. Withdrawal/Discontinuation from the Study

A subject will be withdrawn from the study for any of the following reasons:

- Subject withdrawal of consent.
- Subject not compliant to protocol such as study lens wear time or habitual lens wear while enrolled in the study.
- Subject lost to follow-up.
- Subject no longer meets eligibility criteria (e.g. the subject becomes pregnant).
- Subject develops significant or serious adverse events necessitating discontinuation of study lens wear.
- Subjects who have experienced a Corneal Infiltrative Event (CIE).
- Investigator's clinical judgment regarding the subject safety reasons (that it is in the best interest of the subject to stop treatment).
- Subject missed a study visit.

# **Clinical Study Protocol**

## **Johnson & Johnson Vision Care, Inc.**

- Subject not compliant with study lens wear schedule (i.e. wears study lenses less than at least 6 hours per day for at least 5 days a week over the 2 week wear period)
- Subject not successfully dispensed due to lack of efficacy and safety including poor vision, poor comfort or unacceptable fit.

For discontinued subjects, the Investigator will:

- Complete the current visit (scheduled or unscheduled).
- Complete the Final Evaluation, indicating the reason that the subject was discontinued from the study.
- Record the spherocylindrical refraction with best corrected distance visual acuity.
- Collect used test article(s) (worn or brought to the visit) from the subject and discard them, unless otherwise stated in section 7.2.
- Collect all unused test article(s) from the subject.
- Make arrangements for subject care, if needed, due to their study participation

Additional subjects will be enrolled if a subject discontinues from the study prematurely.

In cases where a subject is lost to follow-up, every possible effort must be made to contact the subject and determine the reason for discontinuation/withdrawal. The measures taken to follow up must be documented including two written attempts and a certified letter (or equivalent) as the final attempt.

## **9. PRE-STUDY AND CONCOMITANT INTERVENTION/MEDICATION**

Concomitant medications will be documented during screening and updated during the study.

- Disallowed medications for this study include: medications that may interfere with contact lens wear (see section 9.1). Habitual medications used by successful soft contact lens wearers are considered acceptable.
- Concomitant therapies that are disallowed include: NA

### **9.1. Systemic Medications**

Certain systemic medications are known to have a higher likelihood to interfere with contact lens wear, chiefly by disrupting the tear film.

A summary of disallowed systemic medications is shown in Table 6. Subjects with a history of taking these medications will be allowed to enroll only if:

- The medications have been taken on a continual, routine basis for at least 6 months, and
- The subject has demonstrated successful contact lens wear during this time.

Or:

# Clinical Study Protocol

## Johnson & Johnson Vision Care, Inc.

- The subject was taking the medication on a temporary basis and ceased taking that medication at least 2 weeks prior to signing the informed consent (this is considered sufficient time for the medication to have left the body prior to enrollment).

Subjects with a history of taking medications listed in Table 6 on a long-term, routine basis for less than 6 months will not be allowed to participate in the study.

Table 6: Disallowed systemic medications

Class of Drug	Common Indication(s)	Common Examples
Estrogens (not including contraceptive medication)	Menopause, osteoporosis, vaginitis	Vagifem, Estrace, Climara, Vivelle-Dot, Premarin, Minivelle, etc.
Anticholinergics	Irritable bowel syndrome, Parkinson's disease, peptic ulcer, cystitis, nasal congestion, cold symptoms, overactive bladder, COPD	Bentyl, Spiriva, Atrovent, Hyosyne, Levsin, Symax Fastab, Symax SL, Homax SL, Cogentin, Transderm Scop, etc.
Beta-blockers	Hypertension, angina, heart attack, migraine, atrial fibrillation, adrenal cancer, essential tumor, glaucoma	Toprol XL, Lopressor, Tenormin, Propranolol, Timoptic, Trandate, Inderal LA, etc.
Psychotropics	Antipsychotic (schizophrenia, mania), antidepression, antiobsessive, antianxiety, mood stabilizer, stimulants (ADHD)	Zoloft, Celexa, Prozac, Lexapro, Effexor, Cymbalta, Ativan, Xanax, Desyrel, Wellbutrin, etc.
Vitamin A analogs	Cystic acne	Isotretinoin

Examples of disallowed systemic antihistamines are given in

Table 7. Subjects with a history of taking systemic antihistamines will be allowed to enroll only if:

- They have taken antihistamines continuously for at least 2 weeks, and
- They have demonstrated successful wear while taking the medication

Or:

- They stopped taking the medication for at least 2 weeks prior to enrollment.

# Clinical Study Protocol

## Johnson & Johnson Vision Care, Inc.

Table 7: Disallowed systemic antihistamines

Class of Drug	Common Indication(s)	Common Examples
Antihistamines	Allergic rhinitis, sedation, hives, allergic conjunctivitis, skin allergy, itching, motion sickness	Hydroxyzine, Promethagan, Phenadoz, Vistaril, Claritin, Zyrtec, Astepro, Astelin, Optivar, Allegra, Benedryl, etc.

## 10. DEVIATIONS FROM THE PROTOCOL

Investigator will notify study sponsor upon identification of a protocol deviation. Protocol deviations must be reported to the sponsor within 24 hours after discovery of the protocol deviation. The Investigator will report deviations per IRB/IEC requirements. All deviations will be tracked, and corrective actions implemented as appropriate.

If it becomes necessary for the Investigator to implement a deviation in order to eliminate an immediate hazard to the trial subject, the Investigator may implement the deviation immediately without notification to the sponsor. Within 24 hours after the implemented deviation, the Investigator must notify and provide the rationale to the Sponsor and, as required, the IEC/IRB.

If the deviation potentially impacts the safety of patient or changes the technical integrity of the study, then it must be reported to IEC/IRB. This is a "Major Deviation". Deviations that contradict the information contained in the Informed Consent/Accent forms will be considered Major Deviations.

Minor deviations have no substantive effect on patient safety or technical integrity of the study. They are often logistical in nature.

Protocol waivers are prohibited.

Table 8 lists examples of deviations that will constitute major and minor protocol deviations for this study.

Table 8: Examples of major and minor protocol deviations

**Clinical Study Protocol**  
**Johnson & Johnson Vision Care, Inc.**

Deviation category	Major deviation	Minor deviation
Out-of-window visit	Visit attended 2 days or more than out of visit window defined in study procedures	Visit attended 1 day or fewer out of visit window defined in study procedures
Unanswered PRO questions	For questionnaires where data is related to a primary or secondary endpoint, 2 or more PRO questions are unanswered (i.e., left blank).	For questionnaires where data is related to a primary or secondary endpoint, 1 or fewer PRO questions are unanswered (i.e., left blank).  For questionnaires where data where data is not related to a primary or secondary endpoint, any PRO questions are unanswered (i.e., left blank).
Insufficient wear of study lenses	Subject does not wear study lenses for at least 6 hours on at least 5 days of a study lens wear period.	NA

In the case of a major protocol deviation, the decision of whether or not the subject will be excluded from the Per-Protocol analysis population will be made at the time of cohort review.

## **11. STUDY TERMINATION**

If more than 2 subjects in the investigational soft contact lens group develop serious expected (e.g., definite or probable MK) or unexpected device related adverse events, the study will be suspended. Upon review and consultation with IRB, DMC, and JJVC Safety Management Team , the study may be terminated. This potential stopping rule is established based on our trial involving approximately 200 subjects wearing the investigational soft contact lens for up to 3 years with an assumed MK rate that is below 0.2% per patient-year. The rate of 0.2% per patient year is the established rate for extended wear lenses in adults, which was requested by the FDA as a criterion for evaluating a contact lens for pediatric use in an FDA response to a pre-IDE submission. To be conservative, 200 independent patient years were used in the calculation. The probability of observing 2 cases or more incidents of MK is 0.061, and 3 cases or more incidents of MK is 0.007 (given an MK rate of 0.2% per patient year).

The occurrence of one or more Unanticipated Serious Adverse Device Effect (USADE), or any SAE where the relationship to study agent cannot be ruled out, may result in stopping further dispensing of test article. In the event of a USADE or SAE, the Sponsor may unmask

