# Clinical Study Protocol

## Johnson & Johnson Vision Care, Inc.

### SYNOPSIS

Protocol Title	Validation of senofilcon A with new UV / HEV Filter
Sponsor	JJVC, [name]
Clinical Phase	Clinical trial phase: confirmatory Design control phase: Confirmatory phase, phase 3
Trial Registration	This study will be registered on ClinicalTrials.gov by the Sponsor
Test Article(s)	Investigational Products: senofilcon A with new UV / HEV filter Approved Products: senofilcon A without new UV / HEV filter (ACUVUE OASYS 1-Day)
Wear and Replacement Schedules	Wear Schedule: daily wear Replacement Schedule: daily disposable
Objectives	This study is being conducted to validate that the Test lens meets the customer requirements. Primary Objectives: The Test lens will meet the safety and efficacy requirements of the Design Validation Requirements. Secondary Objectives: The Test lens will meet the Market Preference Requirements.
Study Endpoints	Primary endpoint(s): logMAR acuity, biomicroscopy, fit acceptance, CLUE vision Secondary endpoint(s): CLUE handling, CLUE comfort, situational visual performance – digital devices, and situational visual performance - indoors
Study Design	This is a bilateral, dispensing, randomized, controlled, subject-masked, 2-arm parallel study. Each subject will be bilaterally fitted with one of the two study articles during the course of the study. There will be a total of 2 visits: 1. Visit 1: Screening, baseline evaluation and lens fit #1 2. Visit 2: Follow-up to lens fit #1. Final evaluation See the flow chart at the end of the synopsis table for the schematic of the study visits and procedures of main observations (Figure 1).

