### **3. TARGETED STUDY POPULATION**

#### **3.1. General Characteristics**

Approximately 160 subjects will be targeted to the Test Group and approximately 160 will be targeted to the Control Group. Within each lens group, the intent is to complete 143 (286 total subjects). Enrolled subjects will be habitual wearers of silicone hydrogel spherical contact lenses. All subjects will be the age of  $\geq 18$  and  $< 40$ . Subjects will wear the study contact lenses approximately two weeks each on a daily wear (DW) daily disposable (DD) basis for a total study duration of approximately 14 days (2 weeks) per subject.

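### Section 11 supports its suspension rule with keratitis probabilities for 200 patient-years, while this Test arm accrues about 5.5 to 6.1; and the synopsis and section 11 differ on whether one possibly related serious event must stop dispensing

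*Combined protocol and SAP*

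**What the plan says.** **Suspension rule.** Section 11 suspends the study when more than 2 subjects in the investigational lens group, that is 3 or more, develop serious expected device-related events (MK is the example given) or unexpected ones. It says the rule is "based on our trial involving approximately 200 subjects wearing the investigational soft contact lens for up to 3 years". The assumed rate is explained as follows: "The rate of 0.2% per patient year is the established rate for extended wear lenses in adults", a figure "requested by the FDA as a criterion for evaluating a contact lens for pediatric use". On exposure: "To be conservative, 200 independent patient years were used in the calculation". The result: "The probability of observing 2 cases or more incidents of MK is 0.061, and 3 cases or more incidents of MK is 0.007".

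**This trial.** The synopsis gives "Wear Schedule: daily wear Replacement Schedule: daily disposable". Section 3.1 states "Approximately 160 subjects will be targeted to the Test Group", with 143 per group intended to complete, "for a total study duration of approximately 14 days (2 weeks) per subject". Section 3.2 limits entry to ages 18 to 39. Section 7.2 (step 1.26) dispenses lenses for 13 to 15 days.

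**Single-event rule.** The synopsis (Study Termination row) says that a UADE, or an SAE for which a causal link cannot be excluded, *will* lead to a stop in further dispensing. Section 11 says that one or more USADEs, or an SAE of that kind, *may* do so.

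**The concern.** The probabilities in section 11 are the only quantitative support for the only numerical suspension rule in the protocol. They tell the sponsor, the sites and the IRB how often the rule would be met by MK alone at a reference rate. If they belong to a longer study with a different type of wear, the protocol does not show how the rule behaves in a two-week trial.

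The single-event clause matters because it acts before the third case. MK is listed in section 13.1 as an ocular serious adverse event, so one MK case whose link to the lens cannot be excluded already engages it. Whether dispensing then stops automatically or at discretion should not depend on which page is read. Enrollment runs for 4 weeks per site at about 16 sites, so the answer can decide whether further subjects are fitted.

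**Working it through.** **Step 1. Reproduce the stated figures.** Inputs from section 11: rate 0.002 per patient-year, exposure 200 patient-years.

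- Expected cases: 200 × 0.002 = 0.4.
- Binomial (200, 0.002): P(≥2) = 0.0614 and P(≥3) = 0.0078.
- Poisson (0.4): P(≥2) = 0.0616 and P(≥3) = 0.0079.

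The stated 0.061 matches. The stated 0.007 is 0.0078 truncated. The figures are correct for their own inputs, and the inputs are 200 patient-years.

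**Step 2. Exposure in this trial.** Inputs: 143 completing and about 160 enrolled Test subjects (section 3.1), 14 days each (13 to 15 in section 7.2). Exposure = n × days / 365.25.

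- 143 × 14 / 365.25 = 5.48 patient-years
- 160 × 14 / 365.25 = 6.13 patient-years
- Extremes of the visit window: 143 × 13 / 365.25 = 5.09 and 160 × 15 / 365.25 = 6.57

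At 14 days, the exposure used in section 11 is 200 / 6.13 = 32.6 to 200 / 5.48 = 36.5 times larger.

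**Step 3. Same rate, this trial's exposure.** With m = 0.002 × patient-years and Poisson counts:

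- P(≥1) = 1 − e^(−m)
- P(≥2) = 1 − e^(−m)(1 + m)
- P(≥3) = 1 − e^(−m)(1 + m + m²/2)

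| | Section 11 | 143 subjects, 14 days | 160 subjects, 14 days |
|---|---|---|---|
| Patient-years | 200 | 5.48 | 6.13 |
| Expected MK cases | 0.4 | 0.0110 | 0.0123 |
| P(≥1) | not stated | 0.0109 | 0.0122 |
| P(≥2) | 0.061 | 5.96e-5 | 7.46e-5 |
| P(≥3) | 0.007 | 2.18e-7 | 3.05e-7 |

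Across the 13-to-15-day window, P(≥2) runs from 5.1e-5 to 8.6e-5 and P(≥3) from 1.7e-7 to 3.7e-7.

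**Step 4. What rate would make 0.007 true here?** A Poisson mean of 0.382 gives P(≥3) = 0.007. Dividing by exposure, 0.382 / 6.13 = 6.2% and 0.382 / 5.48 = 7.0% per patient-year, which is 31 to 35 times the assumed 0.2%.

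**Step 5. The single-event texts side by side.** Both address an unanticipated device effect or a serious event with a possible link to the lens. The synopsis makes the stop in dispensing mandatory; section 11 makes it discretionary. Both are current text: the change history for version 2.0 records only the removal of a questionnaire. A sponsor that continues dispensing after such an event complies with section 11 and breaches the synopsis.

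**The case against.** **The threshold may still be sound.** A reader might infer from the very small P(≥3) that the rule can never fire, or that more than 2 subjects is too lax. The documents do not support that. The trigger counts other serious or unexpected device-related events as well as MK, and section 13.1 lists many. The protocol states no false-alarm target against which to fail the rule, and it gives no event rates for the wider set, so any trigger probability for all qualifying events would rest on invented risks. Section 11 also lets the sponsor, the investigator and the IRB act at any time, and requires termination if an event presents an unreasonable risk. This objection stands and limits the point to the stated justification.

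**The 200 patient-years are described as conservative.** They are, but only against the study described, where 200 subjects for up to 3 years could reach 600. This trial cannot approach either figure, so the remark does not rescue the numbers.

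**The dispensing conflict has limited reach.** Serious events go to the sponsor within 24 hours, and section 11 leaves stopping to the sponsor, so the ambiguity sits mainly there. Lenses are supplied at Visit 1 to last until Visit 2, so further dispensing means mainly new subjects and replacement lenses. This is fair, but whether new subjects are fitted is still a real consequence.

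**Two nearby differences are editorial.** A reader might see a second conflict in the synopsis saying the medical monitor *may* discuss the event with the investigator while section 11 says the sponsor *will*; holding the discussion satisfies both. A reader might also see one in section 11 sending the suspension review to a DMC that section 16.4 lists as not applicable. Elsewhere section 11 qualifies the DMC's role as applying only where there is one, and the IRB and the sponsor's safety team still review.

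**Conclusion.** The exposure basis and both MK probabilities in section 11 do not apply to this trial. The exposure is overstated about 33 to 36 times. At the protocol's own 0.2% rate, the chance of 2 or more MK cases is about 6.0e-5 to 7.5e-5 rather than 0.061, and of 3 or more about 2.2e-7 to 3.0e-7 rather than 0.007. This assumes independent cases, a constant rate, full 14-day wear and 143 to 160 Test subjects. It keeps the extended-wear rate for comparability, although the trial uses daily disposable lenses in adults; the package insert in Appendix C says the risk of ulcerative keratitis is greater in extended than in daily wear, so a lower rate would shrink the figures further.

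The synopsis and section 11 also disagree on whether a stop in dispensing is mandatory after one possibly related serious event.

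This does not show that the threshold is unsuitable or that subjects lack protection. No endpoint, estimate or sample size is touched. It is a correction that should be made in the safety-stopping text.

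**What to change.** 1. In section 11, delete the rationale built on 200 subjects, 3 years and 200 patient-years, together with its two probabilities. Restate the probabilities for this trial's Test exposure of about 5.5 to 6.1 patient-years, and say that they cover MK only.
2. Have the sponsor's safety team reconfirm, on that basis, that more than 2 subjects is the threshold they want. A table of trigger probabilities under assumed risks is not needed.
3. State one single-event dispensing rule in identical words in the synopsis and section 11. The choice between mandatory and discretionary is the sponsor's; mandatory is the more protective.
4. As tidying only, qualify or remove the DMC in the suspension review, and align the wording on discussion with the investigator.

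The cost is protocol wording and a short recalculation, with no extra subjects, visits or procedures.

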# **Clinical Study Protocol**

## **Johnson & Johnson Vision Care, Inc.**

the treatment regimen for the subject(s) and will discuss this with the Investigator before any further subjects are enrolled.

The Sponsor will determine when a study will be stopped. The Principal Investigator always has the discretion to initiate stopping the study based on patient safety or if information indicates the study's results are compromised.

JJVC reserves the right to terminate the study at any time for any reason. Additionally, the IEC/IRB reserves the right to terminate the study if an unreasonable risk is determined. The study can be terminated by the Principal Investigator at the individual clinical site due to specific clinical observations, if in their opinion, after a discussion with JJVC, it is determined that it would be unwise to continue at the clinical site.

JJVC (and the IEC/IRB and DMC, if applicable) will evaluate all adverse events. If it is determined that an adverse event presents an unreasonable risk, the investigation, or that part of the investigation presenting the risk, will be terminated as soon as possible.

Should the study be terminated (either prematurely or as scheduled), the Investigator will notify the IEC/IRB and Regulatory Authority as required by local regulatory requirements.

## **12. PROCEDURE FOR HANDLING PRODUCT QUALITY COMPLAINTS**

A Product Quality Complaint (PQC) refers to any written, electronic, or oral communication that alleges deficiencies related to the identity, quality, durability, reliability, safety, effectiveness or performance of test articles after they have been released for clinical trial use.

Potential complaints may come from a variety of sources including but not limited to subjects, clinical research associates (CRA), clinical operations managers (COM), medical monitors, and site personnel, etc. The following are not considered product quality complaints:

- Subject satisfaction inquiries reported via "Subjective Questionnaires" and "Patient Reported Outcomes (PRO)."
- Clinical test articles that are stored improperly or damaged after receipt at the investigational site.
- Lens replacements that occur due to drops/fall-outs.
- Damage deemed by clinicians or clinical staff to be caused by handling by the user, and not indicative of a quality deficiency (i.e. tears, rips, etc.), only in situations where there is no deficiency alleged by the subject.

Within 24 hours of site personnel becoming aware that a PQC has occurred, the PQC must be recorded in the EDC system, which will trigger an automatic email notification to the appropriate COM/CRA and Clinical QA representative. In cases where the EDC system in use is not configured to send automatic notifications or when an EDC system is not used, the COM/CRA is responsible for notifying Clinical QA upon discovery that a PQC has occurred.

# Clinical Study Protocol

## Johnson & Johnson Vision Care, Inc.

Upon receipt of the EDC notification, the COM/CRA will contact the study site to collect additional information which will include:

- Date the complaint was received/recorded in the EDC System (Date of Sponsor Awareness).
- Who received the complaint.
- Study number.
- Clinical site information (contact name, site ID, telephone number).
- Lot number(s).
- Unique Subject Identifier(s).
- Indication of who first observed complaint (site personnel or subject).
- OD/OS indication, along with whether the lens was inserted.
- Any related AE number if applicable.
- Detailed complaint description (scheduled/unscheduled visit, wear time, symptoms, resolution of symptoms, etc.).
- Eye Care Provider objective (slit lamp) findings if applicable.
- Confirmation of product availability for return (and tracking information, if available), or rationale if product is not available for return

Once a complaint is received, it will be assessed by the COM, CRA, or trained site personnel to determine if it is an Adverse Event/Serious Adverse Event (AE/SAE). If the complaint results in an AE/SAE, the COM/CRA, or trained site personnel will follow section 13 of this protocol. If the AE/SAE was potentially the result of a product quality related deficiency, these procedures also applies and will be executed in parallel.

In some cases, a PQC form may be generated in EDC by the site in error. In this event, the PQC forms will be marked “Intentionally Left Blank” or “ILB”. Justification for ILB must be documented.

